5.4 Time point/frame of measurement for primary variable(s)

The primary endpoints will be assessed 1 day after study drug initiation and TAVR. Measurements taken at 7 and 30 days after TAVR will be considered secondary/exploratory.

5.5. Study variable(s)

5.5.a Clinical/Demographic Variables: Demographic and clinical variables will be captured by interview and electronic chart review at study entry.

Figure 2. Trial Design Schematic

5.5.b P2Y12 Platelet Reactivity: Platelet reactivity to adenosine diphosphate (ADP) will be measured as platelet reactivity units (PRU) using the VerifyNow assay (Accriva Diagnostics, San Diego, California) using whole blood collected in a device- compatible citrated tube.

5.5.c Whole Blood Flow Cytometric Analysis of Patient Samples:

Blood samples will be lysed using BD FACS lysing solution (BD, Franklin Lakes, NJ), washed, and stained as Table 2. Compensation will be performed using standard compensation beads (BD Biosciences) and appropriate isotype control antibodies. Flow cytometry will be performed using a MACSQUANT analyzer. Monocyte phenotypes (classical, non-classical inflammatory

CD14+CD16+, non-classical patrolling CD14lowCD16++) will be analyzed by whole blood flow cytometry using antibodies to CD14 and CD16 as we have previously described¹⁶. Specifically, the % inflammatory monocytes is the proportion of inflammatory monocyte to the

Monocyte Panel A					
Target	Fluorochrome	Vendor	Catalog Number	Clone	Dilution
CD14	Pacific Blue	BD Bioscience	558121	M5E2	1:50
Tissue Factor	FITC	Biomedica Diagnostics	4507CJ	23C11	1:50
CD16	PE	BD Bioscience	555407	3G8	1:50
CD62p	Pe-Cy5	BD Bioscience	551142	AK-4	1:50
CD69	Pe-Cy7	BD Bioscience	335792	L78	1:50
CX3CR1	APC	BioLegend	341610	29A-1	1:50
HLA-DR	APC-Cy7	BD Bioscience	335796	L243	1:50
Monocyte Panel B					
Target	Fluorochrome	Source / Vendor	Catalog Number	Clone	Dilution
CD14	Pacific Blue	BD Bioscience	340507	M5E2	1:50
GP IIb/IIIa	FITC	BD Bioscience	347363	PAC-1	1:50
MRP8/14	PE	Novus Biologicals	NBP2-25269PE	48M7C7	1:250
CD41	Pe/Cy5	BioLegend	303708	HIP8	1:50
CD16	Pe-Cy7	BD Bioscience	557744	3G8	1:50
CX3CR1	APC	BioLegend	341610	29A-1	1:50
CD62I	APC-eFluor780	eBioscience	47-0629-42	DREG-56	1:50

sum of classical, inflammatory and patrolling monocytes. The definition of CD16 positive versus negative gating will be based upon a pan-isotype panel. Final values for % inflammatory monocytes will be the mean of the duplicates obtained using panel A and panel B. Monocyte-CD62P+ platelet aggregation will be analyzed as the mean fluorescence intensity (MFI) of P-selection (Monocyte Panel A) and Monocyte- GP IIb/IIIa+ platelet aggregation will be analyzed as the percentage of monocytes which exhibit positive staining for activated IIb/IIIa (PAC-1 antibody- Monocyte Panel B), with total monocytes as the denominator.

5.5.d Blood Collection and Isolation of Peripheral Blood Mononuclear Cells and Plasma: 30 mL blood was collected in tubes containing ethylenediaminetetraacetic acid (EDTA; BD Vacutainer, Franklin Lakes, NJ) and 2 mL in tubes containing 3.2% sodium citrate (BD Vacutainer, Franklin Lakes, NJ). Samples were then maintained at room temperature until processing. Plasma was isolated from the EDTA blood through centrifugation and preserved at -80 degrees Celsius. Peripheral blood mononuclear cells (PBMC) were isolated by Ficoll-Paque Plus (Sigma, St. Louis, MO) density gradient centrifugation, washed, re-suspended in 90% fetal bovine serum (FBS; Gemini, West Sacramento, CA) and 10% dimethylsulfoxide (DMSO; Sigma, St. Louis, MO), and cryopreserved at -150 degrees F.

5.5.e Plasma Cytokine and Immune Biomarkers: Plasma based assays are done using commercially available ELISA and cytokine bead array technology (BD Biosciences).

5.6 Power Calculation and Sample Size Estimate

Our power calculation is based upon the inflammatory co-primary endpoint, using our preliminary data. In preliminary studies of 25 patients undergoing TAVR, the mean proportion of inflammatory monocytes 1 days after TAVR was 20.0% with a standard deviation of 5.0 %. Thus, a total of 60 patients, randomized 30:30 would be expected to have 80% power to detect an absolute effect of 4% (i.e. ticagrelor treated patients having 16 % percent inflammatory monocytes), using a two sided t-test with Type I error of 0.025. Note that we are using Bonferroni correction, to account for two primary outcomes. We expect dropout of randomized patients to be less than 10% prior to the 1 day blood draw. All randomized patients will be analyzed using an intention to treat analysis. We will assess the missing completely at random assumption by comparing results with analyses derived by assuming that the data is missing at random (MAR), and use of multiple imputation approaches.

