Background treatment: Cardiovascular medications will be continued without planned dose titration as per standard after TAVR. Low dose aspirin 81mg once daily will be initiated on the day of TAVR or continued as pre-existing therapy.

Indication: Aortic Stenosis and planned transcatheter aortic valve replacement (TAVR).

Primary Endpoints: P2Y12 platelet responsiveness (PRU) using the VerifyNow assay at 1 day post procedure and the percentage of inflammatory (CD14+CD16+) monocytes (compared to total monocytes) 1 day after TAVR.

Key inclusion criteria: 1) Valvular heart disease and a clinical indication for TAVR, 2) Age of 18 years or older, 3) Capable of informed consent. 4) Planned transfemoral TAVR.

Key exclusion criteria: 1) Prior history of stroke, transient ischemic attack (TIA), or intracranial hemorrhage, 2) Established bleeding diathesis or thrombocytopenia (<150k/dl), 3) End-stage renal disease, 4) Severe hepatic impairment or liver cirrhosis, 5) Pregnancy, 6) Current infection, 7) History of autoimmune disease, 8) Established allergy to contrast agents, thienopyridines, aspirin, or ticagrelor, 9) History of solid organ transplantation, 10) Atrial Fibrillation, DVT, PE or other indication for long term anti-coagulation, 11) Plan for direct aortic access or trans-apical TAVR, 12) Enrollment in another clinical trial, 13) Recent (< 12 months) or active excessive bleeding.

Type of control: Active treatment

Clinical Event Committee: No

Data Safety Monitoring Board Yes

Number of subjects: A total of 60 subjects will be randomized.

3. Introductory Background

Transcatheter Aortic Valve Replacement (TAVR) has emerged as an important alternative to surgical aortic valve replacement. While this technology represents an important advance over medical therapy or surgical AVR in poor operative candidates, the absolute mortality rates remain high, even in the great majority in whom an optimal hemodynamic result is achieved. In the randomized literature, the majority of these patients die within two years and two thirds of these deaths are due to cardiovascular (CV) events¹.

The mechanisms responsible for this limited survival are unclear from the clinical trials completed to date. While persistent valve disease undoubtedly plays a role in a subset of patients, particularly in patients with significant aortic regurgitation, the majority of events are due to non-valve related co-morbidities.

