The central hypothesis of our proposal is that TAVR-induced injury of the diseased native aortic valve leads to platelet deposition and inflammatory cell activation that can be attenuated by the potent anti-platelet and/or pleiotropic effects of ticagrelor. We propose a single center, prospective randomized trial to test the following specific aims:

1. **To determine whether high-potency ADP receptor blockade reduces measures of platelet activation in patients after TAVR.**
2. **To determine whether high-potency ADP receptor blockade mitigates the pro-thrombotic inflammatory response observed after TAVR.**

The co-primary study endpoints will be 1) platelet responsiveness as measured by the VerifyNow assay (platelet reactivity units, PRU) and 2) the proportion of inflammatory monocytes by polychromatic flow cytometry 1 day after TAVR. Secondary endpoints will include other measures of thrombotic and immunologic activation.

5. Study design

This is a single center, prospective, randomized, open label trial with blinded endpoint evaluation.

5.1 Screening, entry, and randomization:

Patients will be screened for inclusion/exclusion criteria as part of their pre-TAVR clinical evaluation (See Table 1). We plan to screen 150 patients per year, of whom 100 are expected to go on to TAVR. We will continue enrollment until 60 patients are randomized. All patients will be required to sign informed consent prior to planned TAVR. The scheme for a participant's movement through the trial is shown in figure 2.

Patients will be randomized in a 1:1 fashion (n=60) to either continue Clopidogrel (300mg load, 75mg daily) or begin Ticagrelor. Patients will receive a 180mg load followed by 90mg twice daily for one month. This will be an open label design given the different frequency of dosing. Decisions regarding the discontinuance of dual anti-platelet therapy after randomization will be at the discretion of the treating physician.

Patients will be seen at 30 days post TAVR per routine clinical practice. At this time, the final blood draw will be obtained. The occurrence of MACE and bleeding events will be determined by history and corroborated by examining relevant medical records. Patients will revert to clopidogrel therapy at this time and the duration of dual anti-platelet therapy will be left to the discretion of the treating physician.

5.2 Blood Biomarker Procurement:

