using an independent samples t-test (or non-parametric test as appropriate), with significance declared for p-values <0.025 . The primary inflammatory endpoint is the percentage of inflammatory monocytes (compared to total monocytes) as a continuous variable 1 day after TAVR. The percentage of inflammatory monocytes in the Clopidogrel and Ticagrelor groups will be compared using an independent samples t-test (or non-parametric test as appropriate), with significance declared for p-values <0.025 . The percentage of inflammatory monocytes will also be compared over multiple time points to determine the trajectory and duration of the immune response, to guide duration of treatment in future studies. The values at baseline, 1 day, and 7 day will be compared within group using exploratory longitudinal mixed models to determine the kinetics of convalescence and between groups to establish whether treatment effects exist. Models that include the 30-day values also will be fit. Time period will be considered both as a continuous covariate (in days), as well as a categorical variable. Inferential interest will focus on treatment by time interaction. These models will also be used to explore the relationship between the level of P2Y12 inhibition and the reduction in inflammatory monocytes between treatments. This relationship could be different given that Ticagrelor is not only a more potent P2Y12 antagonist as compared with clopidogrel but may also have a unique dual mode of action; P2Y12 antagonism complemented with adenosine uptake inhibition.

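### The 80% power in section 5.6 needs a day-1 value from all 60 patients; with 5 of 60 lost, as its dropout expectation allows, power is about 74% (t-test) or 76–77% (normal approximation)

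*Combined protocol and SAP*

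**What the plan says.** All references are to the combined protocol and SAP.

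- **Power (section 5.6).** Preliminary data from 25 TAVR patients gave a day-1 mean of 20.0% inflammatory monocytes with SD 5.0%. From this: "Thus, a total of 60 patients, randomized 30:30 would be expected to have 80% power to detect an absolute effect of 4" percentage points (20% against 16%), "using a two sided t-test with Type I error of 0.025". The 0.025 is a Bonferroni share for two co-primary endpoints.
- **Dropout (section 5.6, same paragraph).** "We expect dropout of randomized patients to be less than 10% prior to the 1 day blood draw".
- **Missing data (section 5.6).** Analysis is by intention to treat. MAR analyses and multiple imputation appear as a check: "We will assess the missing completely at random assumption by comparing results with analyses derived" under MAR.
- **Primary test (section 5.3).** "The percentage of inflammatory monocytes in the Clopidogrel and Ticagrelor groups will be compared using an independent samples t-test", or a non-parametric test where appropriate. No baseline adjustment is mentioned.
- **Timing (section 5.4).** "The primary endpoints will be assessed 1 day after study drug initiation and TAVR". The 7-day and 30-day values are secondary or exploratory.
- **Number randomized.** The synopsis says "A total of 60 subjects will be randomized"; section 5.1 says "We will continue enrollment until 60 patients are randomized"; section 5.8 provides 60 envelopes, 30 for each drug. No section inflates this number for loss or replaces patients who drop out.

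**The concern.** The paragraph states a power and then a dropout expectation, and does not connect the two. If the 80% already depends on every randomized patient having a day-1 value, any loss before that draw takes power below the stated figure. A later visit cannot make up for it, because both primary endpoints are read only at day 1.

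The trial is sized on this endpoint alone, so the figure tells a reader how much weight a null result can bear. A stated 80% implies a 20% chance of missing a true 4-point effect. If the real chance under the plan's own dropout expectation is higher, the plan should say so.

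**Working it through.** **Inputs (section 5.6).** Difference 4; SD 5, so the standardized effect is 4/5 = 0.8; two-sided alpha 0.025; target power 80%; 30 per arm. Dropout below 10% of 60 means at most 5 patients (5/60 = 8.3%), since 6/60 is exactly 10%.

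**Step 1: number required.** By the normal approximation,

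n per arm = 2 × [SD × (z₀.₉₈₇₅ + z₀.₈₀) / difference]² = 2 × [5 × (2.2414 + 0.8416) / 4]² = 29.70, rounded up to 30.

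Sixty is therefore the number of evaluable patients needed. By the t-test the requirement is 31 per arm.

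**Step 2: reproduce the stated power at 30:30.**

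- The standardized shift is 4 / (5 × √(1/30 + 1/30)) = 4 / (5 × 0.2582) = 3.098.
- Normal approximation: Φ(3.098 − 2.241) = 80.4%.
- Two-sample t-test (non-central t, 58 degrees of freedom, non-centrality 3.098): 78.5%.

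The stated 80% is thus the normal-approximation figure with complete data. A two-sided 0.05 level would give 86–87%, so the Bonferroni level was used.

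**Step 3: remove patients.** The formulas are the same, with n₁ and n₂ the day-1 values available in each arm. For example, at 28/27 the shift is 4 / (5 × √(1/28 + 1/27)) = 4 / (5 × 0.2697) = 2.966, and the normal approximation gives Φ(2.966 − 2.241) = 76.6%. The ranges cover all splits of the losses between the arms.

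| Lost before day 1 | Power, t-test | Power, normal approximation |
|---|---|---|
| 0 | 78.5% | 80.4% |
| 1 | 77.7% | 79.7% |
| 2 | 76.9% | 78.9–79.0% |
| 3 | 76.0–76.1% | 78.1–78.2% |
| 4 | 75.0–75.2% | 77.2–77.4% |
| 5 | 74.0–74.3% | 76.2–76.6% |

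**Step 4: isolate the cost of dropout.** Within one method, 5 losses cost:

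- t-test: 78.51 − 74.34 = 4.2 points (28/27) to 78.51 − 73.97 = 4.5 points (30/25);
- normal approximation: 80.43 − 76.56 = 3.9 points to 80.43 − 76.20 = 4.2 points.

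**Step 5: difference detectable with 80% power.**

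| Day-1 values | t-test | Normal approximation |
|---|---|---|
| 30/30 | 4.07 | 3.98 |
| 28/27 | 4.26 | 4.16 |
| 30/25 | 4.28 | 4.17 |

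**Step 6: can the missing-data plan restore the power?** Intention to treat keeps patients in their assigned arm but does not supply an unmeasured value. Imputation could recover some information if baseline predicts the day-1 value. The plan gives no such correlation, specifies an unadjusted two-sample primary test, and presents imputation as a check on the missing-data assumption. Recovery cannot be assumed.

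**The case against.** **The stated figure is not miscalculated.** This is right. For 30:30 with complete data the normal approximation gives 80.4%. The fault is that the dropout expectation is not carried into the figure.

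**Setting 80% against 74% mixes two effects.** This is also right. About 1.5 points (80 to 78.5) come from using the t-test and exist with no dropout. Like for like, the fall is from 80.4% to 76–77%, or from 78.5% to 74%.

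**Five losses is a ceiling, not a forecast.** The plan gives an expectation below 10% and no point estimate. The interval can be short: the first dose is on the morning of TAVR and the draw is at 24 hours. With 1 lost, the normal approximation still rounds to 80%. But the t-test that the plan names is below 80% at every row of the table, and a power statement should cover the range of loss stated beside it.

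**The effect is small beside other uncertainty.** This stands. Assuming normality, an SD of 5.0 from 25 patients has a 95% confidence interval of 3.9 to 7.0, over which t-test power with complete data runs from about 95% to 47%. An SD of about 4.7 would give 80% by t-test at 28/27. That limits the importance of the point, but it does not make the stated power agree with the stated dropout.

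**Dropout is disclosed and imputation is planned.** Both are true, but neither changes the number of observed day-1 values in the primary test.

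**Conclusion.** The concern holds. The 80% applies only if all 60 randomized patients have a day-1 value, and then only by the normal approximation. At the upper end of the plan's own dropout expectation, the chance of missing a true 4-point effect is about 26% by t-test or 23–24% by the normal approximation, against the 20% implied. The detectable difference rises by about 0.2 points on either method.

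This rests on the plan's SD of 5, a common SD in both arms, approximate normality, an unadjusted two-sample test, and losses that simply remove observations. The shortfall is modest and is a matter of stated power only: it introduces no bias and leaves Type I error unchanged. It should be corrected because the figure and the dropout expectation sit in the same paragraph and do not agree.

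**What to change.** Restate the power sentence in section 5.6, for example:

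> With 60 randomized, power for a 4-point difference (SD 5, two-sided t-test, alpha 0.025) is about 79% if all patients have a day-1 value and about 74% if 5 do not. The difference detectable with 80% power is about 4.1 points with complete data and about 4.3 points with 5 values missing.

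If the normal approximation is preferred, name it and give about 80% with complete data and 76–77% with 5 missing, with detectable differences of about 4.0 and 4.2 points.

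The cost is one sentence and a slightly less favourable stated power. No extra patients are needed, and the endpoint, test and alpha stay as they are.

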Our multi-disciplinary group includes members with broad expertise in cardiovascular and immunologic clinical research. The over-arching aim of our collaborative work to date is to identify shared mechanisms of inflammation and thrombosis that correlate with cardiovascular disease. Recent work from our group has focused on the prothrombotic phenotype of activated inflammatory monocytes which are preferentially expanded in both HIV and ACS².

Clopidogrel treated patients following TAVR have a 64.3% rate of platelet hyporesponsiveness (VerifyNow assay, hyporesponsiveness defined as PRU <208)³. In this post-TAVR population (n=28) the median PRU was 244.5 (interquartile range 164.8-290.3). In preliminary experiments, we find a profile of immune activation after TAVR characterized by the expansion of CD14+CD16+ inflammatory monocytes, a marker we and others have found correlates with adverse cardiovascular events^{2,4}. Of note, we have previously demonstrated that inflammatory monocytes express high levels of tissue factor and this feature also correlates with ACS². Thus, post-TAVR patients represent a patient population in which high-potency ADP receptor blockade may provide protection against MACE.

[figure not shown]

Figure 1. Mechanistic hypothesis of TAVR leading to platelet activation and inflammation

Hypothesis

Our hypothesis is that TAVR results in at least three simultaneous CV insults: 1) the abrupt release of severely elevated left ventricular pressure into a non-compliant systemic vasculature leads to generalized endothelial cell activation, 2) the exposure of the pro-thrombotic and neo-antigenic contents of a degenerated aortic valve (known to histologically resemble atherosclerosis), and 3) the exposure of the replacement valve (bovine valve, stainless steel frame, polyester wrap). We propose that these proximate events lead to platelet activation. Given the important link between thrombosis and inflammation governed by platelet-derived mediators and leukocyte-platelet interactions, we further hypothesize that monocyte activation is mediated, at least in part, by platelet-monocyte interactions, which has been shown to induce the expansion of inflammatory monocytes⁵. Given the pro-thrombotic nature of inflammatory monocytes, we suspect a positive feedback loop may exist via the interplay of these thrombotic –inflammatory mechanisms, which may be abrogated via high potency ADP-receptor blockade (Figure 1).

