If our study results indicate an improved thrombotic and immune convalescence with Ticagrelor, we would conclude that the mechanism of inflammation after TAVR is mediated in

part by platelet activation regulated by the P2Y12 receptor. This would form the basis for additional study of the clinical effects of P2Y12 blockade post TAVR, powered for clinical events. Importantly, the findings of this study might also provide mechanistic proof of principle for additional study of P2Y12 blockade in other disorders that carry elevated CV risk in the setting of chronic immune activation. One such population is the vast majority of HIV patients, who achieve controlled viremia but are left with chronic immune activation and elevated CV risk⁶.

Study Drug Background: Ticagrelor

FDA Label: https://www.accessdata.fda.gov/drugsatfda_docs/label/2015/022433s015lbl.pdf

Ticagrelor is approved by the United States Federal Drug Administration (FDA) to reduce the rate of cardiovascular death, myocardial infarction, and stroke in patients with acute coronary syndrome or a history of myocardial infarction. Ticagrelor was studied in the PLATO trial which included patients with acute coronary syndrome, randomized to Ticagrelor or Clopidogrel for 12 months. At 12 months, a composite of death from vascular causes, myocardial infarction, or stroke (the primary endpoint) had occurred in 9.8% of patients receiving ticagrelor as compared with 11.7% of those receiving clopidogrel (hazard ratio, 0.84; 95% confidence interval [CI], 0.77 to 0.92; $P<0.001$). No significant difference in the rates of major bleeding was found between the ticagrelor and clopidogrel groups (11.6% and 11.2%, respectively; $P=0.43$), but ticagrelor was associated with a higher rate of major bleeding not related to coronary-artery bypass grafting (4.5% vs. 3.8%, $P=0.03$), including more instances of fatal intracranial bleeding and fewer of fatal bleeding of other types.

4. Study objectives

Transcatheter aortic valve replacement (TAVR) has been associated with reductions in CV morbidity and death in extreme risk/surgery inadvisable patients, but cardiovascular events rates remain unacceptably high, with mortality rates of 30% and 50% at 1 and 2 years, respectively^{1,7}. Thus, even after successful treatment of aortic stenosis, this population persists with a risk of CV mortality that is 5-fold greater than cohorts studied in contemporary myocardial infarction trials such as PLATO⁸.

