5.9 Blinding

This trial is an open label trial and patients are not blinded. The laboratory staff will receive study samples containing patient study identification numbers but without any identifiers with regard to treatment assignment. Similarly, the analysis of flow cytometric data will be done by laboratory staff blinded to treatment assignment.

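### Optional: Holm instead of a fixed 0.025 per primary endpoint could add between almost nothing and 7.6 points of monocyte power at the same 5% family-wise bound, but false monocyte claims could rise from 2.5% to as much as 5%

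*Combined protocol and SAP*

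**What the plan says.** Section 4 names two primary endpoints, both read at day 1: "The co-primary study endpoints will be 1) platelet responsiveness as measured by the VerifyNow assay", and the proportion of inflammatory monocytes. Section 5.3 compares the arms on each of them "using an independent samples t-test (or non-parametric test as appropriate), with significance declared for p-values <0.025". Section 5.6 sizes the trial on the monocyte endpoint alone at the same two-sided 0.025 and gives the reason: "Note that we are using Bonferroni correction, to account for two primary outcomes". Its inputs are a mean of 20.0%, an SD of 5.0%, an absolute difference of 4 points and 30 patients per arm, for a stated power of 80%. On losses it says "We expect dropout of randomized patients to be less than 10% prior to the 1 day blood draw". No effect size or power is given for PRU, and no section lets alpha pass from one endpoint to the other.

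**The concern.** The plan is correct, so the question is only whether it gives up power that it could have at no cost in patients. Under a fixed 0.025, a clear PRU result does nothing for the monocyte test. Under Holm, once PRU is significant at 0.025, monocytes are tested at 0.05.

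This could matter because the trial is sized on monocytes with no margin. If PRU is significant, an observed monocyte difference between 2.58 and 2.97 points (30 per arm, SD 5) is negative as written and positive under Holm. The stake on the other side is a false monocyte claim. Section 3 says of a favourable result: "This would form the basis for additional study of the clinical effects of P2Y12 blockade post TAVR, powered for clinical events".

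**Working it through.** **Inputs.** From 5.6: difference 4, SD 5, 30 per arm, two-sided 0.025; 27 per arm at the edge of the dropout allowance (30 × 0.9). From section 3, for PRU: "In this post-TAVR population (n=28) the median PRU was 244.5 (interquartile range 164.8-290.3"). If PRU is normal, SD = (290.3 − 164.8)/1.349 = 93.0. These are clopidogrel-treated patients and the sampling day is not stated. The PRU differences of 40 to 100 and the correlations below are assumptions.

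**The plan's own figure.** The standard error is 5 × √(2/30) = 1.291, so the standardised difference is 4/1.291 = 3.098. By normal approximation, power = Φ(3.098 − 2.241) = 80.4%, which reproduces the stated 80%. The exact noncentral t (58 df) gives 78.5%.

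**Power at the two levels, and the ceiling on the gain.**

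| Per arm | Method | 0.025 | 0.05 | Largest gain (points) |
|---|---|---|---|---|
| 30 | exact t | 78.5% | 86.1% | 7.6 |
| 30 | normal | 80.4% | 87.3% | 6.8 |
| 27 | exact t | 73.5% | 82.2% | 8.8 |
| 27 | normal | 75.7% | 83.6% | 7.9 |

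The smallest significant observed difference at 30 per arm is 2.97 points at 0.025 and 2.58 at 0.05.

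**Why the family-wise bound holds.** If neither endpoint differs, any false claim needs the smaller p-value to fall below 0.025, which is the Bonferroni event and has probability at most 5%. If only one endpoint is truly null, a false claim on it needs its p-value below 0.05, again at most 5%. Neither step uses the correlation.

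**Where between zero and 7.6 the gain falls.** The gain is the probability that the monocyte p-value lies between 0.025 and 0.05 while the PRU p-value is below 0.025. With independent endpoints this is 7.63 points × PRU power. With SD 93 in both arms and 30 per arm, PRU power at 0.025 is 27.1%, 58.1%, 84.6% and 96.7% for differences of 40, 60, 80 and 100. For example, 7.63 × 0.581 = 4.4 points. Simulation (400,000 runs per scenario, bivariate normal within arm, t-tests) gives the gain in points:

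| Correlation | PRU diff. 40 | 60 | 80 | 100 |
|---|---|---|---|---|
| 0 | 2.1 | 4.4 | 6.5 | 7.3 |
| 0.5 | 0.9 | 3.0 | 5.7 | 7.2 |
| 0.7 | 0.3 | 2.0 | 5.3 | 7.2 |
| 0.9 | 0.0 | 0.6 | 5.0 | 7.6 |

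With no PRU effect the gain is 0.2 points or less. With an assumed ticagrelor PRU SD of 50 (clopidogrel 93), a difference of 40 gives 3.2, 1.8 and 1.1 points at correlations 0, 0.5 and 0.7, and a difference of 100 reaches the ceiling. Positive correlation is plausible here, since section 3 states "we further hypothesize that monocyte activation is mediated, at least in part, by platelet-monocyte interactions".

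**The price.** With no true monocyte effect, false monocyte claims are 2.5% as written. Under Holm with independent endpoints they are 2.5% + 2.5% × PRU power. Simulated over correlations 0 to 0.7:

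| PRU difference | False monocyte claims under Holm |
|---|---|
| 40 | 3.2–3.6% |
| 60 | 3.8–4.0% |
| 80 | 4.1–4.6% |
| 100 | 4.7–4.9% |
| 200 | 5.0% |

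The same holds in reverse: with a true 4-point monocyte effect and no PRU effect, false PRU claims at correlation 0 are 0.025 + 0.785 × 0.025 = 4.5%.

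**The case against.** Bonferroni for two endpoints is a legitimate choice, it is stated consistently, and the sizing matches it. That stands: this is not an error.

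The gain is also bought with alpha on the same endpoint. Where it nears 7.6 points, PRU is almost certain to be significant and Holm amounts to testing monocytes at 0.05. If monocytes are then null, the actual family-wise error is 2.5% under Bonferroni and 5% under Holm; only the 5% bound is shared. That stands too, and a team may reasonably want the stricter level on its mechanistic endpoint.

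The gain cannot be pinned down from the documents. The PRU SD of 93 assumes normality, yet the quartiles lie 79.7 below and 45.8 above the median, which suggests skew. This weakens the scenario table but not the zero to 7.6 range, which does not use the PRU SD. The power figures assume t-tests and would differ under the non-parametric option in 5.3; Holm's validity would not.

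Finally, the word co-primary can mean that both endpoints must succeed, in which case no alpha split would be needed and Holm would be the wrong tool. The Bonferroni sentence in 5.6 settles this in favour of a claim on either endpoint.

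**Conclusion.** The point holds as an optional improvement. For a 4-point difference with SD 5 and 30 per arm, Holm would raise exact-t monocyte power from 78.5% by an amount between near zero and 7.6 points. At 27 per arm it would raise 73.5% by at most 8.8 points. The gain is large only if PRU differs clearly. It is negligible if PRU barely differs, or if the PRU effect is modest and the endpoints are strongly correlated. The price is a false monocyte claim rate of up to 5% instead of 2.5% when PRU truly differs, still within the 5% family-wise bound. The conclusion rests on reading the plan as allowing a claim on either endpoint. Which side weighs more is for the trial team to decide.

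**What to change.** If the team wants the gain, replace the fixed threshold in 5.3 with this rule: order the two primary p-values; test the smaller at 0.025; only if it is significant, test the larger at 0.05. Add a matching sentence in 5.6 and keep the 0.025 calculation as the sizing basis.

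The plan specifies no intervals for the primary endpoints. If they will be reported, add one sentence saying that for a second-step p-value between 0.025 and 0.05 the 97.5% interval will include zero although Holm declares significance. For example, at 30 per arm and SD 5, an observed difference of 2.8 gives p = 0.034, a 97.5% interval of 2.8 ± 2.97 (−0.17 to 5.77) and a 95% interval of 2.8 ± 2.58 (0.22 to 5.38).

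The cost is one amendment, with no extra patients and no extra family-wise alpha. The downsides are the higher false-claim rate on a single endpoint, the looser match between intervals and tests, and timing. On timing, section 5.9 says "This trial is an open label trial and patients are not blinded", and the documents do not give enrolment status. The change is defensible only if it is documented before any treatment-group comparison of endpoint data is seen. If that cannot be shown, or if the team prefers to hold false monocyte claims at 2.5%, keep Bonferroni.
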